### Pregnancy test

- A serum pregnancy test should only be performed at Visit 1 (Table 6-1) for women of child-bearing potential
- A urine pregnancy test should be performed at all designated visits after Visit 1 (Table 6-1) for women of child-bearing potential

### Hematology tests

- Complete blood count (CBC) including:
  - White blood cell (WBC) count
  - Complete differential (relative and absolute)
  - Hematocrit (Hct), hemoglobin, red blood cells (RBC), platelets
  - Reticulocyte count

### Urinalysis

- Color, clarity, blood, RBCs, WBCs, protein, glucose, ketones, specific gravity, pH, leukocyte esterase, nitrite, microscopic analysis

Note: A urinalysis is not applicable for those subjects who are unable to provide a urine sample (e.g., incontinent subjects). The reason for not completing the urine sample will be documented.

### Urine toxicity screen

- Subjects who test positive for amphetamines may be retested if they agree to abstain from the medication for the length of their participation in the study and if abstinence from medication usage is achieved at least 7 days prior to Visit 2 (Baseline). The repeat test, and any other tests, must be negative [REDACTED]

- Subjects who test positive for benzodiazepines, THC, or opiates may continue in the study and last usage should be noted at Visit 2. In addition, restrictions listed in Appendix A should be followed.

Laboratory evaluations will be completed according to the schedule presented in Table 6-1 and procedures detailed in the study Laboratory Manual. Additional safety testing may be performed at the discretion of the Investigator or designee.

**Table 6-1 Safety Laboratory Evaluations**

Visit	Testsa,b,c
Visit 1 (Screening)	CHEM (including HbA1c, TSH, free T4 reflex), CBC, UA, urine toxicity screen, serum pregnancy test
Visit 2 (Baseline)	CHEM, CBC, UA, urine toxicity screen, urine pregnancy test
Visit 6 (Week 8)	CHEM (including HbA1c), CBC, UA, urine pregnancy test

Abbreviations: CBC=complete blood count; CHEM=clinical chemistry serum tests; UA=urinalysis

a A pregnancy test is only required for women of child-bearing potential.

b An HbA1c test is only required at Visit 1 (Screening) and Visit 6/EOT.

c TSH and free T4 reflex are only required at Visit 1 (Screening).

### **6.3.9 Safety Follow-up**

A 2-week safety follow-up telephone contact is to be completed for all subjects. Subjects will have the following completed via telephone approximately 2 weeks after the last dose of study drug:

- Assessment of concomitant medications/treatments
- Assessment of AEs

Subjects who discontinue early or complete the study should return to standard of care. The Sponsor will provide investigative sites with 3 months of after-study assistance to transition subjects to standard of care therapy after their participation in the study.

### **6.4 Unscheduled Visits**

Unscheduled visits may occur as determined by the Investigator. The following safety assessments generally should be recorded at each unscheduled visit: assessment of AEs, assessment of concomitant medications/treatments, and measurement of vital signs. The Investigator may perform any additional safety evaluations deemed by the Investigator to be clinically indicated.

## **7 ADVERSE EVENTS**

### **7.1 Specification of Safety Parameters**

#### **7.1.1 Definition of Adverse Event**

An AE is defined as “any untoward medical occurrence associated with the use of a drug in humans, whether or not considered drug related” ([US FDA 2012](#)).

An AE can therefore be any unfavorable and unintended sign (e.g., an abnormal laboratory finding), symptom, or disease temporally associated with the use of a drug, without any judgment about causality or seriousness. An AE can arise from any use of the drug (e.g., off-

label use, use in combination with another drug) and from any route of administration, formulation, or dose, including an overdose.

A suspected adverse reaction is any AE for which there is a reasonable possibility that the drug caused the AE.

AEs do not include the following:

- Stable or intermittent chronic conditions (such as myopia requiring eyeglasses) that are present prior to Baseline and do not worsen during the study
- Medical or surgical procedures (e.g., surgery, endoscopy, tooth extraction, transfusion). The condition that leads to the procedure is an AE if not present at Baseline
- Overdose of concomitant medication without any signs or symptoms unless the subject is hospitalized for observation
- Hospitalization for elective surgery planned prior to study (situation where an untoward medical occurrence has not occurred)
- Pregnancy will not be considered an AE, but if it occurs, it will be reported on a pregnancy form

Adverse events will be recorded from the time informed consent is obtained through the duration of the study. All AEs must be either resolved or stable at end of study. If ongoing at the end of the study the subject should be referred for appropriate treatment.

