### **5.1.6 Overdose**

An overdose is a deliberate or inadvertent administration of a treatment at a dose higher than the maximum recommended dose per protocol. It must be reported, irrespective of outcome, even if toxic effects were not observed ([Section 7.4.4](#)). All events of overdose are to be captured as protocol deviations.

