### **Definition of Hospitalization**

Hospitalization is defined by the Sponsor as a full admission to the hospital for diagnosis and treatment. This includes prolongation of an existing inpatient hospitalization.

Examples of visits to a hospital facility that do not meet the serious criteria for hospitalization include:

- Emergency room visits (that do not result in a full hospital admission)
- Outpatient surgery
- Preplanned or elective procedures
- Protocol procedures
- Social hospitalization, defined as admission to the hospital as a result of inadequate family support or care at the subject's primary residence

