#### **7.4.4 Reporting of Overdose**

An overdose is a deliberate or inadvertent administration of a treatment at a dose higher than the maximum recommended dose per protocol. It must be reported to the Sponsor or designee on the Overdose Form within 24 hours of discovery.

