14.6.3 Suicidality

The C-SSRS is assessed at Screening, Baseline, Weeks 2, 4, 6, and Week 8/ET visits.

The event counts and the number and percentage of subjects in each suicide category at any post-Baseline timepoint (including unscheduled and out of window visits), will be summarized descriptively. Suicide categories will be defined as follows.

- Suicidality: Subjects who report at least one post-Baseline occurrence of suicidal behavior or suicidal ideation

- Suicidal ideation: Subjects who report at least one post-Baseline occurrence of the following
 - wish to be dead
 - non-specific active suicidal thoughts
 - active suicidal ideation with any methods (not plan) without intent to act
 - active suicidal ideation with some intent to act, without specific plan
 - active suicidal ideation with specific plan and intent
- Suicidal behavior: Subjects who report at least one post-Baseline occurrence of the following
 - Preparatory acts or behavior
 - Aborted attempt
 - Interrupted attempt
 - Actual attempt
 - Suicide

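### The adverse event definition leaves out symptom-free concomitant-drug overdoses without regard to intent, so a deliberate overdose can be counted on the C-SSRS yet be absent from the AE and serious AE tables

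*Protocol*

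**What the plan says.** Protocol 7.1.1 opens its list of exclusions with "AEs do not include the following". One item is "Overdose of concomitant medication without any signs or symptoms unless the subject is hospitalized for observation". The general definition in the same section does allow an AE to arise from any "formulation, or dose, including an overdose", but it speaks of the drug; the exclusion concerns concomitant medication only.

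Protocol 5.1.6 and 7.4.4 define an overdose as "a deliberate or inadvertent administration of a treatment at a dose higher than the maximum recommended dose per protocol". Of such an event, 7.4.4 says: "It must be reported to the Sponsor or designee on the Overdose Form within 24 hours of discovery". Section 5.1.6 also makes every overdose a protocol deviation.

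Under Protocol 7.1.2, seriousness is a classification given to an AE. The visits to a hospital facility that do not count as hospitalization begin with "Emergency room visits (that do not result in a full hospital admission". The paragraph on medically significant events adds that the Investigator or Medical Monitor may judge other events serious.

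SAP 14.1 builds its treatment-emergent and serious treatment-emergent tables from reported AEs, up to 30 days after the last dose. SAP 14.6.3 separately tabulates "Suicidal behavior: Subjects who report at least one post-Baseline occurrence of the following", and the list that follows includes an actual attempt.

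**The concern.** Every subject enters with a HAMD-17 total of at least 15. A subject may be taking a background SSRI or SNRI (Inclusion 7) and a short- or medium-acting benzodiazepine (Appendix A). Exclusion 17 removes active suicidality and attempts in the previous 2 years, but not all earlier ideation or behavior: SAP 8.2 plans to report how many subjects had either within the past 6 months. The C-SSRS is a declared safety endpoint.

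In this population, a rule that keeps some overdoses out of the AE record should separate an accidental extra tablet from a deliberate act, and this one does not. Two things are at stake. Sites may differ in whether they record the same event. And one study report could show an actual attempt in its suicidality table with no corresponding entry in its AE tables, because no supplied text asks for the two sources to be compared.

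**Working it through.** The point turns on wording, and the plan gives no figure to reproduce. Setting the texts side by side:

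1. **Does the bullet reach deliberate overdose?** It says nothing about intent. Where the protocol defines the word (5.1.6, 7.4.4), the definition covers deliberate and inadvertent administration alike. A consistent reading therefore brings deliberate overdose within the exclusion.

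2. **Which events are affected?** Only those that meet three conditions together: the drug is a concomitant medication, there are no signs or symptoms, and the subject is not admitted. An emergency room visit that ends in discharge does not meet the hospitalization definition, so it does not bring the event back in. Pimavanserin overdose is outside the bullet.

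3. **What follows for the tables?** If the event is not an AE, the ordinary seriousness classification is not reached, and the tables in SAP 14.1 have no record to count.

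4. **What other routes are there?**
   - The discretionary clause in 7.1.2 refers to an event rather than an AE, so it can carry this one. It is permissive and does not name suicide attempts.
   - The Overdose Form refers to a treatment above the protocol's maximum dose. Appendix A sets numerical maxima for citalopram, escitalopram and venlafaxine, and Inclusion 7 ties background antidepressants to the approved range, so the form may apply to those drugs. For the permitted benzodiazepines Appendix A asks only for the lowest dose needed and sets no numerical maximum. The form does not itself create an AE, and the SAP has no overdose table.
   - The C-SSRS is given from Screening to Week 8/ET. An event rated as an actual attempt would be counted in SAP 14.6.3.

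5. **What changes after Week 8/ET?** Table S-1 schedules no C-SSRS at Visit 7, and Protocol 6.3.9 limits that call to concomitant medications and AEs. Assume that the last dose falls on the Week 8 target day, Day 57. The treatment-emergent period then runs to Day 57 + 30 = Day 87, and the one scheduled contact is at Day 71, which is 71 − 57 = 14 days after the last C-SSRS. In this period AE collection is the main routine route for a suicide attempt, and the bullet narrows it.

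6. **Illustrative size, assuming 40 treated subjects.** One event is 1/40 = 2.5%. The exact 95% lower limit is 1 − 0.975^(1/40) = 0.06%. The upper limit solves (1 − p)^40 + 40p(1 − p)^39 = 0.025, giving p = 13.2%. If the AE tables show 0/40, the upper limit is 1 − 0.025^(1/40) = 8.8%. These figures show only what one unrecorded event would look like; they estimate no frequency.

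**The case against.** The strongest reply is that the bullet excludes an overdose, not a suicide attempt. Nothing in 7.1.1 forbids recording the attempt itself as an untoward occurrence, the mental state behind it may fairly be called a symptom, and 7.4.1 requires all observed and reported AEs to be recorded. This stands in part: a careful investigator has room to record the event. But the text does not require it, and its literal wording points the other way.

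Four stronger readings are tempting, and the documents do not support them.

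- *The attempt would vanish from the study report.* Through Week 8/ET the C-SSRS table should show it. A deviation listing may show it too if the overdose rule applies.
- *It would come to light only through the C-SSRS.* AEs and concomitant medications are asked about at every visit and at the Week 10 call, unscheduled visits are provided for, and each subject has a study partner.
- *It is removed from expedited reporting.* Under 7.4.2, expedited reporting concerns events that are serious, unexpected and related to study drug. AE status alone would not trigger it.
- *The interval between C-SSRS visits defeats the 24-hour SAE rule.* That rule runs from discovery, not occurrence, and AE questions are asked at the same visits. Changing the bullet would not bring detection forward.

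Finally, parts of Protocol 4.4, 7.1.2 and 9.9 are redacted or not in the supplied text, including the section on suicidal ideation and behavior named in the table of contents. An exception or a reconciliation step could sit there. That limits certainty and is not a fault in the plan.

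**Conclusion.** The concern holds in a narrow form. The exclusion, read literally and with the protocol's own meaning of overdose, does not require a deliberate, symptom-free overdose of a concomitant drug without admission to be recorded as an AE. Such an event can be absent from the treatment-emergent and serious treatment-emergent tables while appearing as an actual attempt under SAP 14.6.3. The harm is inconsistent AE and SAE capture rather than loss of the suicidality endpoint, and it is greatest after Week 8/ET.

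The conclusion assumes that the investigator follows the bullet as written, does not use the discretionary SAE clause, and finds no exception in text not supplied. For the mismatch with the C-SSRS it also assumes that the rater codes the act as an actual attempt. The documents give no expected frequency, so no rate of missed events can be stated. Efficacy results, sample size and error rates are unaffected. It is worth correcting because the population is depressed and the correction is small.

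**What to change.** In Protocol 7.1.1, limit the bullet to accidental overdose of concomitant medication. Add a sentence that an intentional overdose of any medication is recorded as an AE whatever its effects, and is assessed for seriousness under the existing criteria in 7.1.2. In SAP 14.6.3, add a listing that matches each post-Baseline C-SSRS suicidal behavior to an AE record and shows any without a match. It would help to state in 5.1.6 and 7.4.4 whether the Overdose Form applies to concomitant drugs.

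The cost is a short wording change, one further listing, and possibly one or two more AE or SAE records. No dose, visit, eligibility rule or analysis model changes. The listing cannot detect events after Week 8/ET, when there is no scheduled C-SSRS to match; for that period the protection comes from the revised AE wording.

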### 7.1.2 Definition of Serious Adverse Event

In addition to the severity rating, each AE will be classified by the Investigator as “serious” or “not serious.” The seriousness of an event will be defined according to the applicable regulations and generally refers to the outcome of an event. An SAE is one [REDACTED] or [REDACTED]

- Is fatal [REDACTED]
- Is immediately life threatening
- Results in disability or permanent damage
- Requires hospitalization
- Prolongs existing hospitalization
- Is a congenital anomaly or birth defect (in an offspring)
- Is medically significant

### **Definition of Life Threatening**

A life threatening event places the subject at immediate risk of death from the event as it occurred. This does not include an AE, which, had it occurred in a more severe form, might have caused death.

### **Definition of Hospitalization**

Hospitalization is defined by the Sponsor as a full admission to the hospital for diagnosis and treatment. This includes prolongation of an existing inpatient hospitalization.

Examples of visits to a hospital facility that do not meet the serious criteria for hospitalization include:

- Emergency room visits (that do not result in a full hospital admission)
- Outpatient surgery
- Preplanned or elective procedures
- Protocol procedures
- Social hospitalization, defined as admission to the hospital as a result of inadequate family support or care at the subject's primary residence

### **Definition of Disability or Permanent Damage**

Disability is defined as a persistent or significant incapacity or substantial disruption of the ability to conduct normal life functions.

### **Definition of Medically Significant**

Important medical events (medically significant events) that may not result in death, be life threatening, or require hospitalization may be considered to be an SAE when, based upon appropriate medical judgment, they may jeopardize the subject or may require medical or surgical intervention to prevent one of the outcomes listed in this definition. Examples of such events are intensive treatment in an emergency room or at home for allergic bronchospasm, blood dyscrasias, or convulsions that do not result in hospitalization or development of drug dependency or drug abuse.

An SAE may also include any other event that the Investigator or Medical Monitor judges to be serious or that suggests a significant hazard, contraindication, side effect, or precaution.

## 7.2 Classification of an Adverse Event

### 7.2.1 Severity of Event

The severity of each AE will be graded on a 3-point scale and reported in detail as indicated on the eCRF:

**Mild:** awareness of sign or symptom but easily tolerated, causing minimal discomfort, and not interfering with normal everyday activities

**Moderate:** sufficiently discomforting to interfere with normal everyday activities

**Severe:** incapacitating and/or preventing normal everyday activities

### 7.2.2 Relationship to Study Drug

The causality of each AE should be assessed and classified by the Investigator as “related” or “not related.” An event is considered related if there is a reasonable possibility that the event may have been caused by the study drug under investigation (i.e., there are facts, evidence, or arguments to suggest possible causation).

**Consider the following when assessing causality:**

- Temporal associations between the agent and the event
- Response to cessation (de-challenge) or re-challenge
- Compatibility with known class effect
- Known effects of concomitant medications
- Pre-existing risk factors
- A plausible mechanism
- Concurrent illnesses

The start and stop dates for AEs will be recorded using the following criteria:

- **Start:** Date of the first episode of the AE or date of significant sustained worsening in severity
- **Stop:** Date when AE either ceased permanently or changed in severity

#### 7.2.2.2 Frequency

The frequency of the AE should be indicated according to the following definitions:

- **Single:** Experienced once, without recurrence

- **Recurrent:** More than one discrete episode with the same severity

#### 7.2.2.3 Action Taken with Study Drug

- **Dose not changed:** No change in study drug
- **Drug interrupted:** Study drug temporarily stopped
- **Drug withdrawn:** Study drug discontinued permanently

#### 7.2.2.4 Therapy

- **None:** No new treatment instituted
- **Medication:** New treatment initiated as a direct result of AE
- **Other:** Other action required

#### 7.2.2.5 Outcome

- **Recovered/resolved:** Recovered or resolved
- **Recovered/resolved with sequelae:** Recovered or resolved with sequelae
- **Not recovered/not resolved:** Not recovered or not resolved
- **Fatal:** Death related to AE
- **Unknown:** Unknown

#### 7.2.2.6 Seriousness

- Not serious
- Serious

#### 7.2.3 Definition of Unexpectedness

An AE, the nature or severity of which is not consistent with the information provided in the reference Safety Information section of the current pimavanserin IB.

#### and Follow-up

In the event that a subject is withdrawn from the study because of an AE, the subject should be followed and treated by the Investigator until the AE has resolved, stabilized, or a new chronic baseline has been established.

### 7.4 Reporting Procedures

#### 7.4.1 Adverse Event Reporting

The Investigator must record all observed AEs and all reported AEs. At each visit, the Investigator should ask the subject a nonspecific question (e.g., "Have you noticed anything

different since your last visit?") to assess whether any AEs have been experienced since the last report or visit.

Note that any use of medication (and specifically any newly prescribed medication) during the course of a study may indicate the occurrence of an AE that may need to be recorded on both the AE and the concomitant medication page.

All AEs will be coded by Data Management using MedDRA.

All AEs, serious and not serious, will be recorded on the AE eCRF page using appropriate medical terminology. Severity and relationship to study drug will be assessed by the Investigator.

When possible, clinical AEs should be described by diagnosis and not by symptoms (e.g., "cold" or "seasonal allergies" instead of "runny nose").

All AEs, *whether or not related to the study drug*, must be fully and completely documented on the AE eCRF and in the subject's notes.

#### **7.4.2 Serious Adverse Event Reporting**

The reporting of SAEs by the Sponsor to the Regulatory Authorities is a regulatory requirement. Each Regulatory Authority has established a timetable for reporting SAEs based upon established criteria.

Serious AEs must be reported within 24 hours of discovery to the Sponsor or its designee; use the appropriate form for initial and/or follow-up reporting.

At a minimum, events identified by the Sponsor to require expedited reporting as serious, unexpected, and related to study drug must be brought to the attention of the responsible Institutional Review Board/Ethics Committee (IRB/EC). These will be provided by the Sponsor after their assessment. For European Union member states, the Sponsor or its designee will provide reports of suspected unexpected serious adverse reactions directly to the ECs, as required by local legislation. In all other countries, it is the Investigator's responsibility to provide these expedited reports to the responsible IRB/EC. It is also the Investigator's responsibility to notify the responsible IRB/EC regarding any new and significant safety information.

For this study, sites will complete the paper SAE, Pregnancy ([Section 7.4.3](#)) and/or Overdose ([Section 7.4.4](#)) form (for initial and/or follow-up information) including available supporting documentation relevant to the event and fax or email (within 24 hours of discovery) to the contact information provided on the SAE, Pregnancy, and Overdose forms.

Subjects will be followed until Visit 6/Safety Follow-up for any SAEs and/or other reportable information or until such events have resolved or the Investigator, in conjunction with the Sponsor, deems them to be chronic or stable.

In the event of any SAE (other than death), the study subject will be instructed to contact the Investigator (or designee) using the telephone number provided in the ICF. All subjects experiencing an SAE will be seen by the Investigator or designee as soon as is feasible following the report of the SAE.

Serious AEs occurring after the study Follow-up Period should be reported if in the judgment of the Investigator there is “a reasonable possibility” that the event may have been caused by the product.

SAEs should also be reported to the IRB/EC according to local regulations.

